## 5. STUDY DESIGN

### 5.1. Overall Study Design

This is a global, multicenter, open-label, single-arm, Phase 2 study of the PI3K $\delta$  inhibitor ME-401 in subjects with relapsed/refractory FL or MZL. ME-401 will be administered orally

at a dose of 60 mg given once a day. A cycle of treatment is 28 days in duration. Treatment with ME-401 is administered based on an intermittent schedule (IS).

The IS includes:

- continuous daily therapy for the initial 2 cycles of treatment
- the intermittent treatment begins at Cycle 3, with ME-401 administered daily for the first 7 days of every 28-day cycle (7 days on treatment and 21 days off treatment)

The first day of treatment is designated as Day 1. ME-401 will be administered until progressive disease (PD), development of unacceptable toxicity (despite ME-401 modified dosing schedule), or subject withdrawal.

Review of the ongoing Phase 1b study evaluating different dosing schedules for ME-401 in subjects with relapsed/refractory FL showed improved risk-benefit profile of the IS over a continuous schedule (CS, i.e., ME-401 given daily continuously). With Amendment 2, the initial CS treatment arm was terminated, and subjects were enrolled to receive therapy on the IS only. If subjects already completed 2 initial cycles of therapy, they were switched to IS dosing once they completed therapy in the ongoing cycle of treatment, and if they had not yet completed the first 2 cycles of therapy they were switched to IS dosing after completion of the first two cycles of therapy. Subjects who progress on IS dosing may be switched to CS dosing.

Upon confirmation of meeting eligibility criteria, subjects are enrolled and should be treated with ME-401 within a reasonable time frame (within 5 days). It is important to ensure that subjects continue meeting protocol specified eligibility criteria to enroll in the study, and if there are >7 days between screening laboratory assessments and expected Cycle 1 Day 1 dosing, then the laboratory assessments should be repeated and reviewed prior to the first dose of ME-401.

The study schema is presented in [Figure 1](#).

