Disease/response assessment will be based on radiological tumor evaluation of neck, chest, abdomen, and pelvis by using IV (and oral, if indicated, per Imaging Manual) contrast enhanced CT/magnetic resonance imaging (MRI) and/or PET-CT imaging modalities at screening and at follow-up visits at the frequency described in the Schedule of Assessments ([Appendix 1](#)), and disease response will be based on the Modified Lugano Classification response criteria ([Appendix 5](#)). Please see [Table 7](#) for overall guidance on response assessment criteria based on Lugano Classification response criteria. In this clinical study, additional modifications to the Lugano Classification response criteria are incorporated per regulatory request to clarify rules for partial response (PR) assessment. These modifications highlight that morphologic (CT scan based) response will be the basis for PR assessment and not metabolic (FDG-PET scan) based assessment of response. Please see [Table 8](#) for details regarding combined response assessment criteria based on beforementioned modified Lugano Classification. For subjects followed by CT scans only, a bone marrow biopsy will be required to confirm a CR in a subject who achieve a morphologic CR by CT scan. To rule out a potential of false positive diagnosis of disease progression in ambiguous cases, it is highly recommended to repeat imaging assessments within 4-8 weeks after initial suspicion of PD. The Investigator's assessment of disease response will be used for subject management. For the final analysis of study efficacy endpoints, disease/response assessment will be performed by an IRRC blinded to Investigator assessment. For subjects with gastric MZL, endoscopy with biopsy must be performed to confirm CR.

Safety will be assessed by laboratory safety tests including hematology (complete blood count [CBC]), serum chemistry, and cytomegalovirus (CMV) using quantitative PCR; and clinical assessments including physical examination, vital signs, ECOG performance status, and 12-lead electrocardiogram (ECG). Adverse events will be graded according to National Cancer Institute Common Terminology Criteria for Adverse Events (NCI CTCAE) v5.0.

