### **5.7. Discontinuation of ME-401 Treatment**

Administration of ME-401 will continue unless one of the following occurs:

- Progressive disease, unless the Investigator deems a switch to continuous dosing is in the best interest of the subject and the subject agrees to continue treatment with CS dosing
- Unacceptable AE(s) considered related/possibly related to ME-401 despite appropriate therapy and modified dosing schedule
- Withdrawal of consent by the subject
- Changes in the subject's medical condition that render further administration of ME-401 unacceptable in the judgement of the Principal Investigator or Sponsor
- Non-compliance
- Termination of study by Sponsor

Subjects who discontinue from therapy should be followed for efficacy and survival unless they withdraw consent to participate.

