For those subjects who switch to CS after disease progression on the IS, the date of PD will be designated as a new baseline, and subsequent response assessments will be scheduled per the protocol-specified frequency ([Appendix 1- Response Assessment](#)): every 2 months for the first 6 months, then every 3 months during the next 12 months up to month 18, and every 6 months thereafter. The date of PD and CT scan at PD will be the new baseline date and CT scan for reference for assessment of recapture of response. The determination that a subject has experienced disease progression should be based on the results of a diagnostic quality CT or FDG-PET scan performed with contrast. Please refer to the Schedule of Assessments for details ([Appendix 1](#)).

To rule out a potential of false positive diagnosis of disease progression in ambiguous cases, it is highly recommended to repeat imaging assessments within 4–8 weeks after initial suspicion of PD. In case of unequivocal disease progression, repeat of scans is not necessary.

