##### **3.2.2. Duration of Response (DOR) and Duration of Recaptured Response (DORR)**

DOR is defined as time from first (CR or PR) response to the time of first PD (based on the Modified Lugano Response Criteria) or the date of death due to any cause (whichever occurs earlier).

For Primary Analysis and NDA Analysis for FL, DOR will be analyzed based on the patients who achieved PR or CR prior to first PD, that is reported before the data cutoff date for the FL Primary Analysis.

As a supportive analysis for NDA Analysis for FL, DOR will be analyzed based on all patients who achieved PR or CR prior to first PD, that is reported before the data cutoff date for the NDA Analysis for FL submission.

To evaluate the duration of response for subjects who had recapture of response on the CS dosing ([Section 3.2.6](#)), DORR is defined as the time from recapture of response (CR or PR) to the time of second PD or the date of death due to any cause (whichever occurs earlier).

Detailed censoring rules are specified in [Table 2](#) (FDA guidance [[FDA 2015](#)] and [[FDA 2018](#)]). In general, in primary analysis for DOR and analysis for DORR, subjects will be censored at the date of last adequate assessment with evidence of no progression by the IRRC, in the following situations:

- No progression nor death
- Discontinuation for any reason other than IRRC documented PD or death, including loss to follow-up, toxicity, withdrawal of consent, etc.
- Start of new anti-lymphoma treatment without evidence of IRRC documented PD
- Death or progression after two or more consecutive missed scheduled visits.

Supportive analysis for DOR will be conducted to evaluate the robustness of the primary analysis result for DOR, by considering all progressions and deaths as events per European Medicines Agency (EMA) guidance ([EMA 2013](#)), regardless of whether they occurred after initiating next anti-lymphoma treatment, after 2 or more consecutive missed scheduled assessments, or being reported as clinical (non-IRRC reviewed radiographic) progression ([Table 3](#)).

For subjects in IS dosing switching to the CS at PD, both DOR and DORR will be estimated.

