**Table 3: Censoring Rules for the Supportive Analysis of DOR**

Situation	Date of Event or Censoring	Outcome
Progression documented	Date of earliest assessment which revealed progression determined by the IRRC	Event
Death before first PD assessment	Date of death	Event
Death between adequate assessment visits	Date of death	Event
No progression, nor death	Date of last adequate assessment with evidence of no progression by the IRRC	Censored
Treatment discontinuation for any reason other than documented PD or death	Date of last adequate assessment with evidence of no progression by the IRRC	Censored
Loss to follow-up	Date of last adequate assessment with evidence of no progression by the IRRC	Censored
Switching back to CS dosing schedule without evidence of PD by IRRC prior to switching *	Date of earliest assessment which revealed progression determined by the IRRC or death after switching to CS	Event
New anti-lymphoma treatment started *	Date of earliest assessment which revealed progression determined by the IRRC or death	Event
Death or progression after two or more consecutive missed scheduled visits *	Date of earliest assessment which revealed progression determined by the IRRC or death	Event
Investigator claim of clinical progression leading to treatment discontinuation *	Date of clinical progression	Event

\* Outcome definitions are different from primary analysis of DOR

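### When the IRRC has not called the progression that led to a switch to CS, neither IRRC DOR analysis counts it, so the supportive analysis only partly tests the primary censoring

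*SAP*

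**What the plan says.** **Endpoint.** SAP 3.2.2: "DOR is defined as time from first (CR or PR) response to the time of first PD", or to death if that comes earlier.

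**Who triggers the switch.** Protocol 5.1: "The Investigator's assessment of disease response will be used for subject management", and "Subjects who progress on IS dosing may be switched to CS dosing". Protocol 2.3 describes continued dosing on CS after progression was confirmed radiographically. Protocol 5.7 lists the switch as the exception to stopping ME-401 at progression: "Progressive disease, unless the Investigator deems a switch to continuous dosing is in the best interest of the subject".

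**Primary IRRC DOR (SAP Table 2).** A subject who switches with no prior IRRC PD is censored at the last adequate IRRC assessment before the switch.

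**Supportive IRRC DOR (SAP Table 3).** For the same subject the date is the "Date of earliest assessment which revealed progression determined by the IRRC or death after switching to CS", with outcome Event. An asterisk marks the row as a deliberate difference from the primary analysis. Only the last row accepts an Investigator's progression, and its condition is "Investigator claim of clinical progression leading to treatment discontinuation".

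**Stated aim of the supportive analysis.** SAP 3.2.2 presents it as a robustness check that takes all progressions and deaths as events, whether they follow new therapy, follow missed visits, "or being reported as clinical (non-IRRC reviewed radiographic) progression".

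**The concern.** SAP 1.2 ties the final DOR analysis to the NDA, and Protocol section 3 states the objective as the efficacy and safety of the IS regimen. If the Investigator judges that a responder has progressed on the IS and moves the subject to CS, that judgement is evidence that the response on the IS has ended. Censoring just before that point may be informative, because such subjects are plausibly nearer to IRRC progression than those who stay on the IS.

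A supportive analysis meant to test robustness should show how much depends on this choice. Here it replaces the censoring with follow-up through CS dosing. Disease control gained on CS then adds to the reported duration for these subjects, and a reader could take agreement between the two analyses as stronger reassurance than it is.

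**Working it through.** **Rule trace.** The plan states no figure on this point, so there is none to reproduce. Take a responder on the IS with Investigator PD who switches to CS.

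| Situation | Table 2 (primary IRRC) | Table 3 (supportive IRRC) | Investigator DOR |
|---|---|---|---|
| IRRC PD at or before the switch | Event at IRRC PD | Event at IRRC PD | Event at Investigator PD |
| No IRRC PD before the switch; IRRC PD or death later | Censored before the switch | Event at the later IRRC PD or death | Event at Investigator PD |
| No IRRC PD before the switch; neither later | Censored before the switch | Censored, later | Event at Investigator PD |

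The last two rows are the point. The third follows because Table 3's date cell needs an IRRC PD or a death; without one, the row for subjects with neither progression nor death applies. Table 3's last row does not reach these subjects: it needs a clinical progression that ends treatment, whereas here treatment continues (Protocol 5.7) and the progression was radiographic (Protocol 2.3).

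**Size (illustration only).** Simulated responders were analysed under three rules: event at the Investigator PD, Table 2 and Table 3. The estimate is Kaplan-Meier at 12 months, S(12) = ∏(1 − d/n) over event times up to 12 months, with d events among n at risk. PD is dated at the next scheduled scan (study days 61, 121, 182, 274, 365, 456, 547, 730 and so on; Protocol Appendix 1). A given share of Investigator PDs is assumed to be both unconfirmed by the IRRC and followed by a switch. Every such PD is taken as true.

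- Set A: median DOR 12 months; CS adds a median of 4 or 8 months; 2-monthly scans on CS; cut-off uniform at 12–24 months from first response; 20,000 responders.
- Set B: median DOR 11.2 months (Phase 1b IS group, Protocol 1.6.2.4, used only as a plausible value); first response at Day 61; 30 months of follow-up; mean further time to IRRC PD of 3 or 6 months; 200,000 responders.

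| Set, share | PD counted | Table 3 | Table 2 | Table 3 − counted | Table 2 − counted |
|---|---|---|---|---|---|
| A, 10% | 56% | 58–59% | 59–60% | 2–3 | 3–4 |
| A, 20% | 56% | 60–61% | 62% | 4–5 | 6 |
| A, 30% | 56% | 62–64% | 66% | 6–8 | 10 |
| B, 10% | 53.9% | 55.7–56.5% | 57.5–57.6% | 1.8–2.6 | 3.6–3.7 |
| B, 20% | 54.0% | 57.6–59.1% | 61.5–61.6% | 3.6–5.1 | 7.5–7.6 |
| B, 30% | 54.0% | 59.4–61.8% | 65.6–65.7% | 5.4–7.8 | 11.6–11.7 |

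The order is the same in every row: PD counted, then Table 3, then Table 2. At 20%, Table 3 closes part of the gap between Table 2 and the counted rule. In Set B this is (61.5 − 59.1)/(61.5 − 54.0) = 32% to (61.5 − 57.6)/(61.5 − 54.0) = 52%. In Set A it is (62 − 61)/(62 − 56) = 17% to (62 − 60)/(62 − 56) = 33%.

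**The case against.** **What stands.** Following IRRC PD or death regardless of the switch is a coherent treatment-policy rule, and it matches Table 3's handling of new anti-lymphoma therapy. It answers a question about IS followed by CS, which is legitimate if labelled as such. Investigator DOR is summarised separately and counts these PDs. Types of censoring are to be reported, DOR is secondary, and no hypothesis test is attached to it. The protocol itself warns of false-positive progression in ambiguous cases (5.1, 7.1), so an unconfirmed Investigator PD need not be a true one. These points lower the stakes but do not remove the gap. Investigator DOR also changes the reader, the responders and the response dates, so it cannot isolate the effect of the censoring rule.

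**Stronger readings that a reader might infer, and that the documents do not support:**

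- *That every progression leading to a switch goes uncounted.* An IRRC PD at or before the switch is an event in both tables.
- *That the Event label applies to a switcher with no later IRRC PD or death.* That subject is censored.
- *That the same PD counts if drug is stopped but not if the subject switches.* The last row of Table 3 covers clinical progression. A radiographic PD that the IRRC did not call, followed by stopping drug, appears to fall under discontinuation for other reasons and is censored.
- *That SAP 3.2.2 flatly contradicts Table 3.* Its parenthesis on clinical progression can be read as excluding scans that the IRRC reviewed without calling PD. The tension rests on the claim to take all progressions.
- *That the IRRC re-reads later scans against the switch scan.* Protocol 7.1 says "the date of PD will be designated as a new baseline", but ties the new scan to recapture of response, and SAP 3.2.6 uses it within the recapture definition. Neither says what the IRRC uses for DOR.
- *That the supportive analysis cannot reveal the problem.* It moves in the right direction and recovers part of the gap.

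**Conclusion.** The point holds for responders whose Investigator PD on the IS was not called by the IRRC before the switch to CS. Neither IRRC analysis counts that PD: Table 2 censors before the switch, and Table 3 lets the response run through CS dosing. This sits uneasily with the stated aim in SAP 3.2.2. The supportive analysis therefore bounds the possibly informative censoring in Table 2 only in part, and for these subjects it describes IS followed by CS.

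The rule trace needs no assumption, but the size does. With assumed shares of 10–30%, 12-month DOR lies roughly 2–8 percentage points above the counted analysis under Table 3 and about 3–12 points above it under Table 2. That holds only if the unconfirmed PDs are true PDs; to the extent that they are false positives, the counted analysis is itself too low. The documents give neither a discordance rate nor a switch rate, so a share below 10% and a smaller effect are possible. This should be corrected in the SAP, but it does not touch the primary ORR analysis.

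**What to change.** 1. Leave Table 2 unchanged.
2. Count a switch to CS with no prior IRRC PD as an event at the date of the Investigator PD that led to the switch. Do this either in the Table 3 analysis or, to keep the treatment-policy rule visible, in one added sensitivity analysis beside the current Table 3.
3. Report how many responders switched without a prior IRRC PD.
4. State which baseline or reference scan the IRRC uses to call PD after a switch.
5. Reconcile the SAP 3.2.2 wording with Table 3, so that the text names the progressions that count.

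The last row of Table 3 should not be widened to every Investigator PD that leads to discontinuation. That would turn an IRRC endpoint into one set by whichever reader calls progression first, a larger change than this point supports.

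**Cost.** A few lines of SAP text and one derived date, which should already be on record because Protocol 7.1 uses the PD date as the new baseline. No change to dosing or visits is involved. The supportive estimate becomes less favourable, and may be too low if some Investigator PDs are false positives. It should therefore be read with Table 2 as a range and not as a replacement for it.

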**Figure 1: Study Schema**

a. Screening from Day -28 to Day -1.

b. IS dosing schedule: 60 mg daily for the first 2 cycles (56 days) followed by 60 mg daily for 7 days of every 28-day cycle (7 days on / 21 days off treatment).

c. Follow-up Period will include: 1) EOT/30-Day Safety Follow-up visit will occur 30 ( $\pm 3$ ) days from the last day of study drug treatment. 2) Efficacy Follow-up - for subjects who discontinue study treatment due to reasons other than disease progression or death, response follow up will occur until PD or the start of a new anti-cancer therapy. 3) Survival Follow-up visits will occur every 3 months until death, and will continue for up to 3 years after the last subject is enrolled in the study.

d. Response assessments will be performed every 2 months ( $\pm 7$  days) for the first 6 months, every 3 months ( $\pm 7$  days) during the following 12 months, and every 6 months ( $\pm 14$  days) thereafter (starting with month 18).

Abbreviations: CS = continuous schedule; EOT = End of Treatment; FU = follow up; IS = intermittent schedule; PD = progressive disease.

For subjects who experience hematologic or non-hematologic adverse reactions, please refer to ME-401 toxicity management ([Table 4](#)) and modified dosing schedules in [Section 5.3.1](#).

ME-401 is provided as 60 mg capsules. ME-401 is to be taken orally once a day at approximately the same time each day in accordance with the IS regimen (or CS dosing regimen if switched from IS after PD).

Subjects must receive prophylaxis treatment for *Pneumocystis jirovecii* pneumonia (PJP) as prescribed within this protocol (see [Section 5.4.3](#)).

See the Schedule of Assessments ([Appendix 1](#)) for a detailed list of study procedures.

The Modified Lugano 2014 criteria will be used for response assessment ([Appendix 5](#)). The Investigator's assessment of disease response will be used for subject management. For the primary analysis, disease/response assessment will be performed by an IRRC blinded to Investigator assessment and treatment assignment. Methods for disease/response assessment by the IRRC are described in the IRRC Charter. Disease/response assessment will occur every 2 months for the first 6 months, every 3 months during the next 12 months, and every 6 months thereafter.

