Subjects will continue to receive study drug in accordance with the IS dosing regimen (or CS dosing regimen if switched from IS after PD) until Investigator-assessed disease progression or unmanageable toxicity requiring treatment discontinuation, subject's decision to withdraw their consent to participate on study, or study closure by the Sponsor. A notification to the Medical Monitor will be sent prior to subject discontinuation. The End of Treatment (EOT)/30-Day Safety Follow-up visit will occur 30 ( $\pm 3$ ) days from the last dose of study drug.

Subjects who discontinue study drug will remain in the study with follow-up conducted every 3 months from the last dose of study drug to obtain post-treatment long-term follow-up information on disease status (i.e., change in disease response, progression), start of subsequent therapy, and survival (death). During this post-treatment follow-up phase, all subjects discontinued for reasons other than PD must continue imaging tests to assess disease status, performed per the original protocol-defined schedule for disease/response assessment, or earlier if clinically indicated. Imaging test results will no longer be collected when a subject starts a new therapy or disease progression occurs. The progression will be documented in the post-treatment long-term follow-up phase. Survival follow-up will continue for up to 3 years after the last subject is enrolled in the study.

Plasma samples will be obtained from all subjects to evaluate ME-401 PK and to serve for ME-401 exposure-response and exposure-toxicity modeling. For subjects enrolled at US sites only, blood samples will be obtained for a correlative immune study. See Schedule of Assessments ([Appendix 1](#)) for blood sample collection.

The primary analysis of ORR for FL will occur after the initial 91 consecutive subjects randomized to or assigned to the IS arm, which represent the Primary Efficacy Population (PEP) (except those who discontinue early), have been followed for at least 6 months from the start of study drug. The final analysis of DOR for FL will occur after most responders in the PEP have at least 12 months of follow-up from first response.

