**Figure 1b: Study Schema (Protocol Amendments 2 and 3)**

Abbreviations: EOT = End of Treatment; FU = follow up; PD = progressive disease.

a Screening from Day -28 to Day -1.

b IS dosing schedule: 60 mg daily for the first 2 cycles (56 days) followed by 60 mg daily for 7 days of every 28-day cycle (7 days on / 21 days off treatment).

c Follow-up Period will include: 1) EOT/30-Day Safety Follow-up visit will occur 30 ( $\pm 3$ ) days from the last day of study drug treatment. 2) Efficacy Follow-up - for subjects who discontinue study treatment due to reasons other than disease progression or death, response follow up will occur until PD of the start of a new anti-cancer therapy. 3) Survival Follow-up visits will occur every 3 months until death, and will continue for up to 3 years after the last subject was enrolled in the study.

d Response assessments will be performed every 2 months ( $\pm 7$  days) for the first 6 months of therapy, every 3 months ( $\pm 7$  days) during the following 12 months, and every 6 months ( $\pm 14$  days) thereafter (starting with month 18).

Subjects who discontinue study drug will remain in the study with follow-up conducted every 3 months from the last dose of study drug to obtain post-treatment long-term follow-up information on disease status (i.e., change in disease response, progression), start of subsequent therapy, and survival (death). During this post-treatment follow-up phase, all subjects who discontinued treatment due to reasons other than PD must continue imaging tests to assess disease status, performed per the original protocol-defined schedule for disease/response assessment, or earlier if clinically indicated. Imaging test results will no longer be collected when a subject starts a new therapy or disease progression occurs and is documented in the post-treatment long-term follow-up phase. Survival follow-up will continue for up to 3 years after the last subject is enrolled in the study.

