**Table 2: Censoring Rules for the Primary Analysis of DOR and DORR**

Situation	Date of Event or Censoring	Outcome
Progression documented	Date of earliest assessment which revealed progression determined by the IRRC	Event
Death before first PD assessment	Date of death	Event
Death between adequate assessment visits	Date of death	Event
No progression, nor death	Date of last adequate assessment with evidence of no progression by the IRRC	Censored
Discontinuation for any reason other than documented PD or death	Date of last adequate assessment with evidence of no progression by the IRRC	Censored
Loss to follow-up	Date of last adequate assessment with evidence of no progression by the IRRC	Censored
Switching back to CS dosing schedule without evidence of PD by IRRC prior to switching	Date of last adequate assessment with evidence of no progression by the IRRC before switching back to the CS dosing schedule	Censored
New anti-lymphoma treatment started without evidence of PD by IRRC	Date of last adequate assessment with evidence of no progression by the IRRC before the start of new anti-lymphoma treatment	Censored
Death or progression after two or more consecutive missed scheduled visits	Date of last adequate assessment with evidence of no progression by the IRRC	Censored

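### The new-therapy row of SAP Table 3 reduces to death only, so the supportive DOR analysis leaves the censoring at new therapy essentially untested

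*SAP*

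**What the plan says.** SAP 3.2.2 gives the purpose: "Supportive analysis for DOR will be conducted to evaluate the robustness of the primary analysis result for DOR". Progressions and deaths are to count "regardless of whether they occurred after initiating next anti-lymphoma treatment, after 2 or more consecutive missed scheduled assessments". The section attributes this approach to EMA guidance.

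For a responder who starts new anti-lymphoma treatment:

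- **SAP Table 2 (primary)** censors at "Date of last adequate assessment with evidence of no progression by the IRRC before the start of new anti-lymphoma treatment".
- **SAP Table 3 (supportive)** labels the outcome an event, dated at "Date of earliest assessment which revealed progression determined by the IRRC or death".

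Three places end imaging at that moment:

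- Protocol 5.1: "Imaging test results will no longer be collected when a subject starts a new therapy or disease progression occurs".
- Protocol Figure 1, follow-up note: "response follow up will occur until PD or the start of a new anti-cancer therapy".
- SAP 2.3, text under Figure 1b: "Imaging test results will no longer be collected when a subject starts a new therapy or disease progression occurs and is documented".

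**The concern.** The supportive rule needs IRRC-read scans that the study does not plan to collect. For this row only death remains observable.

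The primary rule is open to informative censoring here. Treatment continues until the investigator assesses progression (Protocol 5.1), while a DOR event in Table 2 requires progression determined by the IRRC. A responder whom the investigator judges to be progressing, but the IRRC does not, can move to new therapy and be censored at the last negative scan, possibly shortly before the IRRC would have called progression. That pushes the Kaplan-Meier curve up. SAP 1.2 names the final DOR analysis as the one supporting the NDA filing, so a check that omits this censoring matters.

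Table 3 also leaves two programming questions open. The row says event but gives no date for a subject who is alive with no observed progression. The same subject can also fall under the row for treatment discontinuation for other reasons, which is censored, and no precedence is stated. SAP 3.2.4 adds to the confusion: it says PFS follows the primary DOR censoring rules but cites Table 3.

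**Working it through.** **Step 1: the changed rows.** Table 3 stars four rows as differing from the primary analysis.

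| Starred row | Needs scans after new therapy? | Can it work? |
|---|---|---|
| Switch to continuous dosing without IRRC progression | No; assessments continue (Protocol 7.1) | Yes |
| Death or progression after two or more missed visits | No | Yes |
| Investigator-claimed clinical progression leading to discontinuation | No | Yes |
| Start of new anti-lymphoma treatment | Yes, for its progression part | Death only |

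Deaths are captured through survival follow-up. Protocol 8.7 and the post-treatment note in Appendix 1 mention long-term imaging without repeating the stop, but they do not override the explicit statements quoted above.

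**Step 2: size, by formula.** The documents give no DOR assumption and no rate of new therapy before IRRC progression, so these inputs are assumed unless a source is named:

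- True DOR is exponential with median 12 months, and first response is at the Day 61 scan.
- Scans follow on Days 121, 182, 274, 365 and 456 (Appendix 1). With 30.4375 days per month (the SAP's conversion) they fall at 1.97, 3.98, 7.00, 9.99 and 12.98 months after response. Data cutoff is 14 months after response.
- A share f of responders (6%, 12%, 18%) starts new therapy 0.5 month after the last negative scan before their IRRC progression.
- A share c of those starters is caught by the clinical-progression row, with the event dated at new therapy.

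Progression-free proportions at the scans are S = 0.5^(t/12) = 0.8924, 0.7948, 0.6675, 0.5616 and 0.4726. Interval progression risks are q = 0.1076, 0.1093, 0.1602, 0.1586 and 0.1586. The share of eventual progressors who start new therapy is g = f/(1 − 0.4726) = f/0.5274, and h = g(1 − c) is the part not caught. Subjects not caught leave the risk set at their last negative scan, so

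KM(12) = 0.5616 / ∏(k=1..4)(1 − h·q_k) × [1 − g·c·q_5/(1 − h·q_5)].

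For f = 12%, g = 0.12/0.5274 = 0.2275.

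- c = 0: 0.5616/[(1 − 0.0245)(1 − 0.0249)(1 − 0.0364)(1 − 0.0361)] = 0.5616/0.8835 = 63.6%.
- c = 1: 0.5616 × (1 − 0.2275 × 0.1586) = 54.1%.

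| f | Table 2 (c = 0) | Half caught | Three quarters caught | All caught, or new therapy as event (c = 1) |
|---|---|---|---|---|
| 6% | 59.7% | 57.4% | 56.3% | 55.1% |
| 12% | 63.6% | 58.6% | 56.3% | 54.1% |
| 18% | 67.7% | 59.9% | 56.4% | 53.1% |

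With no new therapy the value is 56.2%.

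With nobody caught, Table 3 differs from Table 2 only through deaths. A simulation of the same set-up, with 5% of starters dying before cutoff, gives 59.6/63.3/67.6% under Table 2 and 59.4/63.0/67.0% under Table 3, a change of 0.2, 0.3 and 0.6 points.

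**Step 3: a second illustration with other assumptions.** Here IRRC progression has median 12 months, death has median 60 months, follow-up is 18 months, and the intercurrent event falls at 50% to 100% of the time to progression. Counts are per 60 responders (65.5% of 91 is 59.6). With 20% starting new therapy and nothing else:

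| Rule | Median DOR (months) | Events per 60 |
|---|---|---|
| Primary | 11.8 | 35.4 |
| Table 3, death only, others censored at last scan | 11.7 | 36.5 |
| Table 3, death only, others carried event-free to cutoff | 12.9 | 36.5 |
| Start of new therapy as event | 9.5 | 43.8 |

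In the third line the supportive estimate is longer than the primary, the wrong direction for a check on optimism.

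Now add 10% clinical progression, 5% schedule switch and 5% missed visits, with 10%, 20% and 30% starting new therapy. Changing only the new-therapy row moves the median from 12.9 to 12.8, 14.4 to 14.1 and 16.2 to 15.5 months. Applying all rows of Table 3 moves it from 12.9 to 10.4, 14.4 to 11.3 and 16.2 to 12.3.

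**The case against.** A reader might infer that the whole supportive analysis can hardly differ from the primary one and so tests nothing. The documents do not support that. Three of the four changed rows need no scans after new therapy, and Step 3 shows that together they can move the median by 2.5 to 3.9 months under the assumptions used.

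The strongest counter-argument is that the clinical-progression row may catch the very subjects at issue. Someone taken off treatment for investigator-assessed progression before new therapy could count as an event there. With three quarters caught, the bias in Step 2 is gone; with all caught, Table 3 equals the analysis proposed below. This stands as a limit on size. It does not close the gap: SAP 3.2.2 describes that row as clinical progression outside IRRC-reviewed radiography, while Protocol 7.1 sends all imaging to the IRRC, so its coverage of radiographic investigator progression is unclear. The row also misses subjects who stop for toxicity and start new therapy later.

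Other planned outputs help too. SAP 7.2.2 reports DOR by investigator assessment and tabulates types of censoring, so the amount of new-therapy censoring will be visible. Neither output shows what that censoring does to the IRRC-based estimate.

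Two further inferences go too far. One is that new therapy is the main source of informative censoring; the documents give no rate for it, and Table 2 also censors other discontinuations and schedule switches. The other is that the plan misses the full distance between Table 2 and the new-therapy-as-event rule. That distance is measured against a conservative rule, not against the truth.

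Finally, a living subject with neither event could be placed under the row for no progression and no death. That reading is sensible, but Table 3 does not state it.

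**Conclusion.** The point holds for one row. SAP Table 3 asks for IRRC progression after new anti-lymphoma treatment, and the protocol and SAP stop collecting the scans that could show it. The row reduces to death, its outcome for living subjects is unstated, and the primary analysis's censoring at new therapy stays essentially untested. The rest of the supportive analysis works.

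Under the Step 2 assumptions, with no starter caught by the clinical-progression row, Table 2 overstates the 12-month DOR by 3.5 points (59.7 − 56.2) at 6% new therapy and by 11.5 points (67.7 − 56.2) at 18%. Table 3 recovers at most 0.6 of those points. Counting new therapy as an event errs the other way, by 1.1 points (56.2 − 55.1) to 3.1 points (56.2 − 53.1). These figures show direction and range; they are not forecasts for this trial, and the gap shrinks as more starters are caught. DOR is a descriptive secondary endpoint, so no hypothesis test is affected.

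**What to change.** 1. Keep the EMA-style analysis. Rewriting its row so that new therapy is itself the event would contradict SAP 3.2.2, which counts progressions and deaths "regardless of whether they occurred after initiating next anti-lymphoma treatment".
2. Add a second supportive DOR analysis: start of new anti-lymphoma treatment, without earlier IRRC progression or death, is an event at its start date.
3. In Table 3, state that subjects alive without observed progression after new therapy are censored at the last adequate IRRC assessment and are not carried event-free to cutoff.
4. State which row takes precedence when the treatment-discontinuation row and the new-therapy row both apply.
5. Correct the table reference for PFS censoring in SAP 3.2.4, so that the text and the cited table agree.

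The cost is a few lines of SAP text and one more Kaplan-Meier run. Start of subsequent therapy is already collected in follow-up (Protocol 5.1 and 8.7), so no imaging is added. The downside is that the added estimate is conservative, because some new therapy starts without progression: in the Phase 1b monotherapy cohorts, 4 of 22 discontinuations were for stem cell transplant (Protocol 1.6.2.1). It should be read beside the primary estimate, not in place of it.
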